A randomized controlled trial to investigate whether a multifaceted Antimicrobial Stewardship Program can improve adherence to guidelines for diagnosis and treatment of uncomplicated pharyngotonsillitis in primary care

Abstract

Background: In order to achieve a rational use of antibiotics and slow down the development of antibiotic-resistant bacteria, it is important to develop and scientifically evaluate Antimicrobial Stewardship Programs (ASP), the purpose of which is to reduce unnecessary use of antibiotics. Pharyngotonsillitis (sore throat) is one of the most common causes of antibiotic prescription in primary care. Since adherence to guidelines on diagnosis and treatment of pharyngotonsillitis is insufficient, a well-defined, repeatable and scientifically evaluated ASP needs to be developed for this purpose.

Aims and objectives: To develop an ASP for pharyngotonsillitis and evaluate whether this intervention can increase compliance with guidelines for the diagnosis and treatment of pharyngotonsillitis in primary care.

Study Methods: A randomized controlled trial in which 50 primary health care centres (PHCCs) in Västra Götaland are randomized either to an intervention group implementing the newly developed ASP for pharyngotonsillitis or to a control group.

The intervention lasts for six months, including both doctors and nurses and involving reflective meetings on guidelines, didactic patient cases, identification of local improvement opportunities, the establishment of an action plan and recurrent feedback in the form of a lab- and diagnosis-linked prescription statistic for pharyngotonsillitis.

Antibiotic prescription for pharyngotonsillitis is followed up in relation to a rapid antigen detection test (RADT) for group A streptococci (GAS). Primary outcome measure: the proportion of patients with antibiotic-treated pharyngotonsillitis who have a positive RADT for GAS. Change in outcome measures will be compared between the control group and the intervention group at 6, 12 and 18 months.

Expected Results: If the trial shows that this ASP leads to increased adherence to guidelines for pharyngotonsillitis, the implementation of this ASP could lead to more rational use of antibiotics.

Background

Antibiotic-resistant bacteria are becoming more common and constitute one of the biggest threats to our future health [1, 2]. To slow down this development, it is important not to prescribe antibiotics unnecessarily [3]. Pharyngotonsillitis (sore throat) is one of the most common causes of antibiotic prescribing in primary health care centres (PHCCs) [4, 5]. In the clinical everyday life, general practitioners (GPs) experience uncertainty about the treatment of patients with pharyngotonsillitis [6], and adherence to guidelines on diagnostics and treatment of pharyngotonsillitis needs to be improved [4, 7]. The single most important rule-of-thumb in primary care is to normally only prescribe antibiotics for pharyngotonsillitis when a positive rapid antigen detection test (RADT) for beta-haemolytic streptococci group A (GAS) is presented [8, 9].

It is important for GPs to have the opportunity to reflect on their own antibiotic prescribing, to have regular interdisciplinary discussions at the PHCC about antibiotics and guidelines to increase knowledge and understanding of the guidelines and thus feeling confident in the clinical everyday life [10-14]. Structural factors at the PHCC such as the manager's involvement and nurses' work on telephone counselling and on triage reception are also important in achieving a rational use of antibiotics [10]. Antimicrobial Stewardship Programs (ASP) are structured multifaceted interventions to reduce unnecessary antibiotic use and have in many cases led to more rational use of antibiotics within inpatient care [15-17]. There is largely no evidence showing which ASPs are effective in PHCCs, at least from a Swedish perspective since we have a comparatively low rate of antibiotic prescribing [17, 18]. Since pharyngotonsillitis is common and adherence to guidelines is insufficient, there is a need for a well-described, repeatable and scientifically evaluated ASP for pharyngotonsillitis.

Aims and Objectives

To scientifically develop and evaluate an ASP to see if this intervention can increase adherence to guidelines for the diagnosis and treatment of pharyngotonsillitis in primary care.

Research questions

Is there a difference between PHCCs randomized to ASP intervention or control in change from baseline and measurements after 6, 12 and 18 months regarding the following outcomes:

1. the proportion of patients with pharyngotonsillitis prescribed antibiotics (J01 excluding methenamine) having a positive RADT for GAS? (Pharyngotonsillitis is a collective term that covers several diagnostic codes (ICD-10 codes))?
2. the proportion of patients with pharyngotonsillitis and a negative rapid test for GAS prescribed antibiotics (J01 excluding methenamine)?
3. the proportion of patients with pharyngotonsillitis prescribed recommended first-line antibiotics (in Sweden phenoxymethylpenicillin = PcV)?
4. the proportion of patients given a diagnosis of pharyngotonsillitis where CRP was analysed?

The following research questions will not estimate change but rather focus on a description of numbers during the baseline period:

5. the proportion of patients with pharyngotonsillitis prescribed antibiotics where no throat swab was taken

6. the proportion of patients given a diagnosis of pharyngotonsillitis where throat swab culture was analysed?
7. the proportion of patients given a diagnosis of pharyngotonsillitis where a rapid test for mononucleosis was analysed?

Is there a correlation between any change in the proportion of patients with antibiotic-treated (J01 excluding methenamine) pharyngotonsillitis with a positive RADT for GAS and the structural factors in the intervention group:

- the size of the PHCC (number of enlisted patients) and the age profile of enlisted patients?
- the number of patients with pharyngotonsillitis per 1000 enlisted patients and year?
- geographical location (large or mid-sized city versus small village)?
- Adjusted Clinical Group (ACG; a measure for evaluating the enlisted population's state of health)?
- Care-need index (CNI, socio-economic variables)?
- Type of PHCC: private/public?
- staffing (proportion of permanent-employed GPs, Residents, interns and locum tenens)?

Study Methods

Target and Study Population

50 PHCCs in the southwest of Sweden (Västra Götaland Region), volunteering to participate in this project, are randomized either to an intervention group, implementing the newly developed ASP for pharyngotonsillitis, or to a control group.

Inclusion criteria:

- PHCCs located in Västra Götaland with an agreement with Region Västra Götaland (there are about 200 such PHCCs).
- The PHCC has at least 3 medical practitioners (required for reflective meetings to be meaningful).
- The PHCC has an electronic medical record compatible with the data extraction tool MedRave Primary Care.
- The PHCC has a license for the data extraction tool MedRave Primary Care.

Exclusion criteria:

- Newly opened PHCCs that have been in existence for less than one year (excluded because reliable measurement cannot be made at baseline)

Calculation of sample size (power calculation)

Assuming linear regression where the independent variable is the group affiliation (control or intervention), an effect size (Cohen's d) of 0.3, a significance level of 0.05 and a power of 0.95. Under these assumptions, 45 primary care centres are required. In order to have a safety margin, we will strive to include 50 primary care centres.

Study Design

PHCCs randomized to the intervention group

Any PHCC in Region Västra Götaland, Sweden, are required to have a dedicated contact GP to Strama Västra Götaland in order to be eligible for public funding: “The PHCC must have knowledge of current antibiotic resistance data, its adherence to treatment guidelines for infections in primary care and antibiotic prescription. The primary care centre must also appoint ASP physicians who cooperate with, and together with the operations manager, report to Strama Västra Götaland in these areas.”

These physicians, who already have a deep understanding of the issues around antibiotic stewardship, will be responsible for the ASP on their respective PHCC (called “ASP physicians”).

In order to be able to carry out the intervention, the ASP physicians at the PHCCs randomized to the intervention will receive training to lead workshops about diagnosis and treatment of pharyngotonsillitis at their PHCC. The workshops will include a Powerpoint presentation on current guidelines for pharyngotonsillitis, a discussion on a case study of pharyngotonsillitis with didactic questions and a tutor manual, present lab- and diagnosis-linked prescribing statistics of pharyngotonsillitis to their colleagues at the PHCC, to identify areas of potential improvement and to create an action plan based on this, which is then followed up at the PHCC as described below. Strama prepares and provides all the required materials for these workshops. The PHCCs' ASP physicians are trained during the month before the intervention commenced and the training will be held by the project manager and Strama Västra Götaland. Several training opportunities will be offered so that all ASP physicians at the PHCCs in the intervention group will be able to attend the training.

The ASP physician leads a workshop at the PHCC with the following content:

All permanently employed doctors who are on duty at the PHCC will attend the reflective meeting as well as the practice manager of the PHCC's. The reflective meeting is led by the ASP physician. At least one representative of the nurses participates, if possible, all nurses participate in the meetings and also the PHCC's laboratory staff. The reflective meeting includes:

- A PowerPoint presentation, prepared by Strama Västra Götaland, which illustrates guidelines on diagnosis and treatment for pharyngotonsillitis in primary care including a short patient case.
- An extensive discussion around hypothetical cases of patients with pharyngotonsillitis. Didactic questions are posed to facilitate discussion. The discussion is led by the ASP physician who uses a supervisor manual to facilitate the discussion.
- The ASP physician will, before the reflective meeting, extract lab- and diagnosis-linked prescription statistics for pharyngotonsillitis during the past year (using the “tonsillitis module” in the software “Medrave4 Primary care”). These statistics are prepared for the PHCC as a whole and for each individual doctor in the primary care centre to form the basis for self-reflection. The ASP physician presents this data at the workshop. Based on the statistics, the PowerPoint presentation and the discussion of the patient cases, the participants identify which opportunities for improvement are available at their PHCC. This is summarised in a structured form, which is also part of the CRF (Case Report Form). Individual doctors' prescriptions form the basis for self-reflection but are not reported in CRF, where only the PHCC's combined diagnosis-linked prescription statistics are reported for pharyngotonsillitis.
- Based on identified improvement opportunities, the workshop continues with a discussion about suitable measures at the PHCC, in order to improve. The practice manager participates in this discussion. The resulting action plan is documented in the CRF.

Follow-up meetings on primary care centres in the intervention group:

- Every two months, during the intervention process (six months), the ASP physician extracts the PHCC's lab- and diagnosis-linked prescription statistics for pharyngotonsillitis for the last two months. The statistics are presented in a doctor meeting or staff meeting to follow up on the action plan. This statistic is extracted for the PHCC as a whole and for each individual doctor to form the basis for self-reflection. Based on the result, the continued work is adjusted as needed and the ASP physician notes a summary in the PHCC's CRF.
- If questions arise during the intervention, the ASP physician can consult with Strama Västra Götaland.

The control group

PHCCs that are randomized to the control group do not receive any study-related active intervention and the doctor who is responsible for reporting antibiotic prescription statistics to Strama at these PHCCs do not receive the above mentioned ASP training. The PHCCs in the control group, like all other PHCCs in Västra Götaland, participate in the activities that Strama Västra Götaland carries out regardless of this project.

Data collection

Collected data for all PHCCs (intervention group + control group)

The following data is collected for all PHCCs, both in the intervention group and the control group; at the start of the study (when the intervention starts at the PHCCs = baseline), as well as 6, 12 and 18 months after the date when the PHCCs in the intervention group begin the intervention with reflective meetings around pharyngotonsillitis.

Quality indicators for pharyngotonsillitis - measurement period last six months:

- the proportion of patients prescribed antibiotics (J01 excluding methenamine) for pharyngotonsillitis having a positive rapid test for GAS
- the proportion of patients prescribed antibiotics (J01 excluding methenamine) for pharyngotonsillitis having a negative rapid test for GAS
- the proportion of patients prescribed antibiotics (J01 excluding methenamine) for pharyngotonsillitis given first line antibiotics (PcV) according to the national Swedish guidelines
- the proportion of positive rapid test for GAS of all analysed rapid test for GAS among patients with a formal diagnosis of pharyngotonsillitis
- the proportion of patients with a formal diagnosis of pharyngotonsillitis where CRP was analysed
- the proportion of patients with a formal diagnosis of pharyngotonsillitis where throat swab culture was analysed
- the proportion of patients with a formal diagnosis of pharyngotonsillitis where a rapid test for mononucleosis has been analysed

This data is extracted (for the last six months) using the software "Medrave4 Primary care ®" at baseline and after 6, 12 and 18 months. Virtually all PHCCs in Västra Götaland have this software and regularly use it for monitoring quality at the PHCC. In addition, all PHCCs included in this project will check that the rapid test for GAS is registered in the electronic medical record in such a way that the software "Medrave4 Primary Care ®" can identify this.

Structural data required in CRF:

- Staffing at the present time: Number of permanent-employed GPs, Residents, interns, and locum tenens, respectively divided into short-term (<3 months of service) and long-term (\geq 3 months of service) locum tenens.
- The number of patients with pharyngotonsillitis per 1000 patients enlisted at the PHCC at baseline.

Structural data for each participating PHCC

These are obtained from Munin (a quality monitoring software for Primary care in Västra Götaland):

- Type of PHCC: run privately or public?
- the size of the PHCC (number of enlisted patients) and age profile of enlisted patients?
- geographical location (large or mid-sized city versus small village)?
- the number of patients with pharyngotonsillitis per 1000 enlisted patients and year?
- Adjusted Clinical Group (ACG); a measure for evaluating the enlisted population's state of health)?
- Care-need index (CNI); socio-economic index of patients enlisted at the PHCC

Data processing

Descriptive statistics

Descriptive statistics (a measure of central tendency and probability distribution) will be presented for the all previously stated research questions at the start of the study (when the intervention starts at the PHCCs = baseline) and after 6, 12 and 18 months.

Comparisons at baseline

Comparative statistics (chi-two tests and t-tests pending on variable type) will be performed to identify differences between the intervention group and the control group at baseline.

Estimation of change

Any change between the data for the 6 months prior to the intervention (when the intervention starts at the PHCCs = baseline) and measurement after 6, 12 and 18 months, respectively, is calculated for each PHCC regarding the following outcome measures:

Primary outcome measure

1. the proportion of patients with antibiotic-treated (J01 excluding methenamine) pharyngotonsillitis having a positive rapid test for GAS

Secondary outcome measures

2. the proportion of patients with pharyngotonsillitis and a negative rapid test for GAS prescribed antibiotics (J01 excluding methenamine)
3. the proportion of antibiotic-treated (J01 excluding methenamine) patients with pharyngotonsillitis treated with recommended antibiotic according to guidelines (PcV)
4. the proportion with pharyngotonsillitis diagnosis where CRP was analysed
5. the proportion of patients with pharyngotonsillitis prescribed antibiotics where no throat swab was taken
6. the proportion with pharyngotonsillitis diagnosis where throat swab culture was analysed
7. the proportion with pharyngotonsillitis diagnosis where a rapid test for mononucleosis has been analysed.

Regression analysis

A) Investigate if the intervention is effective

To investigate whether a change in outcome measure 1-4 differs between the intervention group and the control group, linear regression is performed where adjustment is made for any variables that differ at baseline. A regression is performed for each individual outcome measure at follow-up after 6, 12 and 18 months. Change in the respective outcome measures compared to baseline is used as a dependent variable. Group affiliation (intervention group or control group) will be used as an independent variable. Independent variables will also be the following covariates taken from baseline measurement: the number of enlisted patients at baseline, location in cities versus small villages, Adjusted Clinical Group (ACG), Care-need index (CNI) and type of PHCC (private/public).

B) Investigate if structural factors are associated with maintaining the effect of the intervention

To study if there is a relationship between more permanent change in the proportion of patients with antibiotic-treated (J01 excluding methenamine) pharyngotonsillitis who had a positive rapid test for GAS (primary outcome measure) and structural data in the intervention group, regression analysis will be done.

Change between baseline and follow-up data (18 months after initiation of intervention) for the proportion of patients treated with antibiotics for pharyngotonsillitis who have had a positive rapid test for GAS is used as a dependent variable. The following independent variables will be used:

the number of patients with pharyngotonsillitis per 1000 enlisted patients and year, the proportion of PHCCs located in cities versus small villages, Adjusted Clinical Group (ACG), Care-need index (CNI) and type of PHCC: (private/public), at baseline.

Expected results and significance

This study is expected to shed light on whether a well-defined ASP intervention can increase adherence to guidelines for the diagnosis and treatment of pharyngotonsillitis in primary care. If so, the implementation of this ASP could lead to improved diagnostics and more rational use of antibiotics in pharyngotonsillitis in primary care. In order to be able to slow down the increasing trend with an increasing proportion of resistant bacteria, it is important to avoid unnecessary antibiotic treatments.

The intervention will be well described so that it can be repeated elsewhere if the evaluation shows that the intervention is effective. The planned intervention is time-efficient in that the Strama group educates one ASP physician from each PHCC so that they, in turn, carry out the intervention at their respective PHCC.

References

2. WHO: **The evolving threat of antimicrobial resistance - Options for action**. Geneva: World Health Organization; 2012.
3. Davies J, Davies D: **Origins and evolution of antibiotic resistance**. *Microbiol Mol Biol Rev* 2010, **74**(3):417-433.

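### Forty-five PHCCs give about 17% power for Cohen's d = 0.3, not the 95% stated; the figure of 45 fits f² = 0.3, which is d = 1.10

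*Combined protocol and SAP*

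**What the plan says.** The section on calculation of sample size gives the model as "Assuming linear regression where the independent variable is the group affiliation (control or intervention"), with "an effect size (Cohen's d) of 0.3, a significance level of 0.05 and a power of 0.95". It then states: "Under these assumptions, 45 primary care centres are required". The target is raised slightly: "In order to have a safety margin, we will strive to include 50 primary care centres".

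The section does not state whether the test is one- or two-sided, the allocation ratio, a standard deviation, the software, or any variance explained by covariates. The target population section says only that PHCCs "are randomized either to an intervention group, implementing the newly developed ASP for pharyngotonsillitis, or to a control group". On PHCCs holding an agreement with the region, the inclusion criteria note that "there are about 200 such PHCCs".

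Under Regression analysis, part A, the dependent variable is each PHCC's change from baseline. The PHCC is therefore the unit of analysis, and d must be read on the scale of PHCC-level change.

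**The concern.** A standardised difference of 0.3 normally calls for several hundred units, so 95% power from 45 is implausible on sight. This calculation is the plan's only justification of the trial's size, and its inputs and result contradict each other within one paragraph.

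The consequence is mainly one of interpretation. The plan tells readers that an effect of d = 0.3 would almost certainly be detected. If the trial finds no significant difference, a reader relying on that statement could conclude that the programme has no effect of that size, when the trial had little chance of showing one. The margin from 45 to 50 PHCCs also appears to protect power that the design does not have at d = 0.3.

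**Working it through.** **Inputs.** From the sample size section: d = 0.3, "a significance level of 0.05", "a power of 0.95", one predictor (group), N = 45 in total, 50 sought. Assumed because not stated: two-sided test, 1:1 allocation. Alternatives are tried in step 5.

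**1. The plan's own figure, from its stated inputs.** Regression on one binary predictor is the two-sample t-test, with N − 2 degrees of freedom and noncentrality d·√(n₁n₂/N).

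Normal approximation for total N with equal arms:

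N = 4(1.960 + 1.645)² / d² = 4 × 12.995 / 0.09 = 577.5, or 289 per arm (578).

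The exact noncentral t gives 290 per arm, **580 in total**. The stated 45 is not reproduced: 580 / 45 ≈ 13.

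**2. Power at the stated and planned sizes, d = 0.3, two-sided, exact.**

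| PHCCs | Noncentrality | Power |
|---|---|---|
| 45 (22 + 23) | 0.3 × √(22 × 23 / 45) = 1.006 | 16.6% |
| 50 (25 + 25) | 0.3 × √(25 × 25 / 50) = 1.061 | 18.0% |
| 200 (100 + 100) | 0.3 × √(100 × 100 / 200) = 2.121 | 56.0% |

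The last row takes every PHCC with a regional agreement. The other criteria can only reduce that number. For d = 0.3, 80% power needs 352 PHCCs and 90% power needs 470.

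**3. Where 45 probably comes from.** In regression power software the effect size is often Cohen's f², with noncentrality λ = f²·N on 1 and N − 2 degrees of freedom. Setting f² = 0.3 and solving for 95% power gives N = 45.33. Power is 0.949 at N = 45 and 0.953 at N = 46.

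With equal arms, f² = d²/4. Hence:

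- f² = 0.3 means d = 2√0.3 = 1.095
- d = 0.3 means f² = 0.09 / 4 = 0.0225

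On the d scale the two differ by 1.095 / 0.3 ≈ 3.65.

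**4. What 50 PHCCs can detect** (two-sided, 1:1, unadjusted): d = 0.81 at 80% power, 0.94 at 90%, 1.04 at 95%. Deducting five degrees of freedom for the named covariates raises these values by 0.002 to 0.003.

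**5. Other readings of the stated inputs.**

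| Reading | Result |
|---|---|
| One-sided test | 484 PHCCs for 95%; power 25.6% at 45, 27.5% at 50 |
| 45 per arm, two-sided | power 29% |
| Total 45, allocation 1:4 to 3:1, two-sided | power 12% to 17%, highest at 1:1 |
| One-sample or paired test | 147 (two-sided) or 122 (one-sided) |
| 0.3 as Cohen's f (f² = 0.09) | 147 |
| 0.3 as a correlation | about 139 |
| 0.3 as R² | 33 |

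Of the readings tried, only f² = 0.3 lands near 45.

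**The case against.** The strongest counter-argument concerns covariates. The planned model adjusts for five baseline variables and for any others that differ at baseline. If d is defined on the unadjusted SD, the variance they explain raises power. This is correct, but it does not rescue the figure. If they explained half the variance in change, the effective d would be 0.3 / √0.5 = 0.424 and power with 45 PHCCs about 29%. Reaching 95% would need R² = 1 − (0.3 / 1.100)² ≈ 0.93, where 1.100 is the d detectable with 45 PHCCs at 95% power. The plan assumes no such reduction. It does follow that the detectable values in step 4 describe the unadjusted comparison and should be labelled so.

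Sidedness and allocation are indeed unstated, so the 17% is conditional on a two-sided test and equal arms. The most favourable alternative, a one-sided test, still leaves power below 28%.

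The f² explanation is an inference. The plan names neither f² nor any software, and strict rounding up would give 46 rather than 45. This limits what can be said about the cause, not the finding that d = 0.3, 45 PHCCs and 95% power cannot all be true.

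It is also fair to say that the plan never calls 0.3 the smallest important difference and does not say how a null result will be read. The risk of misreading is therefore a possibility, not a certainty.

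**Conclusion.** The concern holds. With two-sided alpha 0.05 and equal arms, the design has 16.6% power for d = 0.3 at 45 PHCCs and 18.0% at 50, against the 95% claimed. It would miss an effect of that size about 82% of the time with 50 PHCCs, or about 73% with a one-sided test. The number required for the stated inputs is 580 (484 one-sided), beyond the roughly 200 PHCCs with a regional agreement. No sidedness, allocation or per-arm reading of the stated inputs comes near 95%, and nothing elsewhere in the document redefines the 0.3.

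The most probable explanation is a mislabelled f². In that case the trial was sized for d of about 1.1, and the plan offers no argument that an effect that large is plausible. This must be corrected, because the stated power is wrong by a wide margin and is the sole basis for the trial's size.

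**What to change.** Rewrite the sample size paragraph and leave the number of PHCCs unchanged.

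- State which effect-size metric was entered, the software, the sidedness and the allocation ratio.
- Replace the power statement. Assuming two-sided testing and equal arms, suitable text is: *With 50 PHCCs randomised 1:1 and a two-sided test at 0.05, the unadjusted comparison detects d = 0.81 with 80% power and d = 1.04 with 95% power. Power for d = 0.3 is about 18%.*
- If the sponsor confirms that f² was used, add: *The figure of 45 PHCCs was obtained with f² = 0.3, equivalent to d = 1.10, for which power at 45 is 94.9%.*
- Translate the detectable d into percentage points of the primary outcome (d × SD) and say whether such a difference is plausible. The analysed variable is change, so the SD of PHCC-level change is the one needed. The documents do not give it. Two successive six-month extractions before baseline could supply it; failing that, the baseline SD between PHCCs could serve as an approximation.
- Commit to interpreting a non-significant result by its confidence interval, without appeal to the planned power.

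The cost is one rewritten paragraph and, at most, one extra routine data extraction. Outcomes and the analysis model do not change. The stated power becomes less favourable.

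### The intervention arm's six-month baseline includes the month in which its ASP physicians are trained, which may slightly dilute the change scores toward no effect

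*Combined protocol and SAP*

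**What the plan says.** All references are to the combined protocol and SAP.

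- **Training.** Under Study Design, in the part on PHCCs randomised to the intervention, ASP physicians "will receive training to lead workshops about diagnosis and treatment of pharyngotonsillitis at their PHCC". The same paragraph gives the timing: "ASP physicians are trained during the month before the intervention commenced". Several sessions are offered. The section on expected results adds that "the Strama group educates one ASP physician from each PHCC".
- **Time zero.** Data collection counts the 6-, 12- and 18-month points from "after the date when the PHCCs in the intervention group begin the intervention with reflective meetings around pharyngotonsillitis". The clock therefore starts with the meetings at the PHCC, not with the training.
- **Baseline window.** Data collection gives the heading "Quality indicators for pharyngotonsillitis - measurement period last six months". Estimation of change, under Data processing, is more explicit: "Any change between the data for the 6 months prior to the intervention (when the intervention starts at the PHCCs = baseline".
- **Use of the baseline.** Regression analysis, part A: "Change in the respective outcome measures compared to baseline is used as a dependent variable".
- **Control arm.** The section on the control group states that the corresponding physicians there are not given the training.

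No washout, exclusion of the training month or sensitivity analysis is described.

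**The concern.** A baseline for a change score should be measured before either arm is exposed to anything that could move the outcome. Here the sections combine to put up to one month of possible exposure inside the baseline of one arm only. The training concerns the same guidelines, cases and prescribing statistics that the physician will later present to colleagues, so it could plausibly affect how that physician prescribes.

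If it does, the intervention arm's baseline share of RADT-positive patients among those treated is raised, and its measured change is lowered by the same amount. The control arm has nothing to offset this. All three follow-up times share the one baseline, so all would be affected alike. The direction is toward no effect: what is at stake is some understatement of benefit and some power, not a false positive finding.

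**Working it through.** **Step 1: the overlap.** Set side by side, the sections give training in the last month before time zero, time zero at the reflective meetings, and baseline as the six months ending at time zero. The training month is thus 1 of 6 baseline months, or 16.7% of the window. It is post-randomisation, because the physicians trained are those at PHCCs already allocated to the intervention.

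**Step 2: dilution formula.** Let p be the untreated proportion, Δ the full effect, and q the share of Δ already present, on average, across the training month. With equal case numbers per month (assumption):

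- intervention baseline = (5/6)p + (1/6)(p + qΔ) = p + qΔ/6
- follow-up = p + Δ
- change = Δ(1 − q/6)

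The proportional dilution is D = q/6, where q = (part of the month after training) × (trained physician's share of prescribing) × (share of the full effect produced by training alone).

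**Step 3: inputs.** The documents give one trained physician per PHCC and, in the inclusion criteria, "The PHCC has at least 3 medical practitioners". With equal prescribing load (assumption) the trained physician's share is therefore at most 1/3. The documents do not give the exact training dates or the effect of training alone, so a range is shown.

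| Assumption | D | An assumed 10-point effect appears as |
|---|---|---|
| Training alone changes nothing | 0% | 10 |
| One of three prescribers, mid-month on average, half the effect: 1/6 × 1/2 × 1/3 × 1/2 | 1.4% | 9.9 |
| One of three, mid-month on average, full effect: 1/6 × 1/2 × 1/3 | 2.8% | 9.7 |
| One of three, whole month, full effect: 1/6 × 1/3 | 5.6% | 9.4 |
| Ceiling: whole PHCC, whole month, full effect: 1/6 | 16.7% | 8.3 |

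**Step 4: the plan's own sample size.** The plan states an effect size of 0.3 labelled Cohen's d, significance level 0.05, power 0.95 and 45 PHCCs. A two-sided comparison of two means with d = 0.3 needs 289 per arm, 578 in total, so 45 does not follow from that label. Reading 0.3 as the regression effect size f² (one tested predictor, two-sided 5%, noncentral F) gives N = 46, with power 0.949 at N = 45. This approximately reproduces the stated figure and is used below. For equal arms it corresponds to d = 2√0.3 = 1.10.

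**Step 5: effect on power at 50 PHCCs.** The noncentrality is λ = 0.3 × 50 × (1 − D)².

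| D | λ | Power |
|---|---|---|
| 0 | 15.00 | 0.967 |
| 2.8% | 15 × (35/36)² = 14.18 | 0.958 |
| 5.6% | 15 × (17/18)² = 13.38 | 0.948 |
| 16.7% (ceiling) | 15 × (5/6)² = 10.42 | 0.885 |

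At 5.6%, keeping the same power would need about 1/(17/18)² = 1.12 times as many PHCCs. The planned margin is 50/45 = 1.11.

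**The case against.** The strongest reply is that nothing in the documents says the training changes prescribing. It is training to lead workshops, given to one physician per PHCC who, by the protocol's own account, already understands stewardship well. The components aimed at the whole PHCC (the meeting, the feedback of statistics to colleagues, the action plan and the two-monthly follow-up) all come at or after time zero. This stands, and it is why the dilution is conditional and may be zero.

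Three stronger readings are tempting, and the documents do not support them.

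- **That part of the effect is certainly subtracted, or that a full sixth of the baseline is post-training.** Only the overlap is certain. Sessions are spread over the month, so one sixth is the upper limit for post-training time.
- **That dilution near 16.7% is a realistic scenario.** It would need colleagues who have not yet attended any meeting to show the whole effect for the whole month. Even 5.6% assumes the smallest eligible PHCC, training on the first day and the full effect from training alone.
- **That the affected baseline distorts the covariate adjustment.** The covariates named in analysis A are structural (list size, location, ACG, CNI, ownership), and training one physician cannot move them. The plan also adjusts for variables that differ at baseline, but does not say that these include a prescribing measure.

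It is also fair to say that the margin of 50 over 45 PHCCs absorbs nearly all the loss at 5.6%, and that a positive result would stand. What remains is a possible one-sided bias whose size the planned analyses do not estimate.

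**Conclusion.** The point holds as a minor one. As written, the plan gives a baseline that is not fully pre-exposure in the intervention arm, with no counterpart in the control arm. If training alone changes the trained physician's prescribing, the estimated effect at 6, 12 and 18 months is diluted toward no effect.

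The documents give no figure for that influence. The range of 0% to about 5.6%, and about 2.8% with training mid-month on average, rests on three assumptions: only the trained physician changes, prescribing load is equal among at least three practitioners, and cases are spread evenly over the months. The power figures also assume 1:1 allocation, a two-sided test and f² = 0.3. On those terms the cost is one to two percentage points of power. A reader should not infer that an effect has been shown to be lost, or that the trial's conclusions are endangered.

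**What to change.** In Data collection and in Estimation of change, define baseline as the six months ending the day before the first ASP-physician training session, with the same calendar window for all PHCCs in both arms. Keep the 6-, 12- and 18-month windows anchored to the start of the reflective meetings.

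This is a cheap improvement of about one sentence. The indicators are extracted retrospectively from the records. The window reaches back about seven months before time zero (6 + 1), and PHCCs open for less than a year are already excluded, so the data should exist.

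The downside is that baseline and the 12-month window no longer cover the same calendar months. The offset is about one month and is equal in both arms, so any seasonal difference should largely cancel in the comparison between arms. A sensitivity analysis that repeats the primary regression with the window as the plan now defines it would show whether the choice matters. If the main definition cannot be changed, a sensitivity analysis leaving out the training month in both arms is a reasonable fallback.
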